5.3 Definition of Dose-Limiting Toxicity N/A

5.4 General Concomitant Medication and Supportive Care Guidelines:

5.4.1 Standard supportive therapies currently employed for radiation side effects will be administered in conventional dose, including anti-diarrheal medication (Imodium, Lomotil) anti-

CONFIDENTIAL

This document is confidential. Do not disclose or use except as authorized.

emetic medication (Ativan, Zofran, Reglan, Compazine, etc.), colony stimulating factors, transfusions, etc. as required to provide optimal medical symptom management and support of study participants. No experimental medications or off-label medications will be employed.

Transfusion of red blood cells to maintain hemoglobin >10 g/dl will be employed at discretion of treating physician and medical team in the case of hemoglobin <10 g/dl at study entry and in the eventuality that hemoglobin declines during the course of protocol therapy.

5.5 Duration of Therapy

Duration of therapy will depend on evidence of disease progression and tolerance. In the event of a treatment break for circulating blood counts (neutrophils, platelets) to recover, treatment will resume when counts have recovered per section 5.1.2. The treatment break will be documented in the data set; any length of break to allow blood counts to recover is allowed. In the absence of treatment delays due to adverse events, treatment may continue until completed or until one of the following criteria applies:

- Disease progression outside of the radiation target volume,
- Intercurrent illness that prevents further administration of treatment,
- Unacceptable adverse event(s), including grade 4 thrombocytopenia or neutropenia; grade 3 hemoglobin, diarrhea, urinary frequency, or fatigue; or grade 2 weight loss.
- Participant decides to withdraw from the study, or
- General or specific changes in the participant's condition render the participant unacceptable for further treatment in the opinion of the treating investigator.

5.6 Duration of Follow Up

Participants will be followed for 60 months after completion of protocol therapy or removal from study or until death, whichever occurs first. Participants removed from study for unacceptable adverse events will be followed until resolution or stabilization of the adverse event. Participants who experience a recurrence of their disease will be followed for survival only after the recurrence.

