5.7 Criteria for Removal from Study

CONFIDENTIAL

This document is confidential. Do not disclose or use except as authorized.

Participants will be removed from study when any of the criteria listed in Section 5.5 applies. The reason for study removal and the date the participant was removed must be documented in the study-specific case report form (CRF). Alternative care options will be discussed with the participant.

In the event of unusual or life-threatening complications, participating investigators must immediately notify the Principal Investigator:

[name] at [contact] or

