6.1 Anticipated Toxicities

Acute toxicities expected from conventional photon therapy administered alone, or with concurrent chemotherapy, to the pelvis or extended volume (pelvic and para-aortic nodal basins) are listed below. Because radiation will be administered to a smaller volume using proton beam, acute toxicities are expected to be delayed in onset and/or milder in severity. Recovery from acute side effects is expected over a 3-6 week period after the last treatment has been administered.

Acute (temporary) effects include:

Likely (more than 50% chance this will happen):

- Fatigue
- Cramps
- Frequent bowel movement
- Diarrhea
- Nausea
- Urinary frequency and urgency
- Burning with urination
- Vaginal irritation with itching and discharge
- Skin reaction (radiation dermatitis)
- Rectal irritation

Frequent (10-50% chance this will occur):

- Nausea (mild) and vomiting (rare) that is treatable with medications.
- Reduction in circulating blood counts including red cells which are important for carrying oxygen, platelets which are important for normal blood coagulation, and white cells which are important in fighting infection. If severe, changes in circulating blood counts may require blood transfusion, hospitalization, and medication intended to bring blood counts to normal levels.

Occasional (Between 1-10% chance this will occur):

- Dehydration and Electrolyte imbalances (changes in body salts) may occur in patients experiencing nausea, vomiting and diarrhea. This may not cause symptoms but sometimes causes fatigue, muscle weakness, muscle cramps, irregular heart beat or seizures. This can be severe and possibly life threatening, and may require hospitalization and intravenous treatment.

Delayed effects which may develop after completion of Proton beam radiation treatment include:

Frequent (10-50% chance this will occur):

- Leg lymphedema (swelling of legs due to a block in lymphatic flow)

CONFIDENTIAL

This document is confidential. Do not disclose or use except as authorized.

Occasional (Between 1-10% chance this will occur):

- Bowel obstruction requiring surgery to repair.
- Bowel injury
- Premature menopause: probable if ovaries have not been conserved surgically and removed to locations remote from the radiation target volumes.
- Bone fractures in the pelvis or spine
- Weight loss is slow and progressive and rarely exceeds 10% of pre-protocol treatment weight.

Rare (Less than a 1% chance this will occur):

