All patients will be followed for a minimum of 60 months following completion of protocol therapy.

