14.3 Stratification Factors: N/A

14.4 Analysis of Secondary Endpoints:

CONFIDENTIAL

This document is confidential. Do not disclose or use except as authorized.

Secondary endpoints are QOL, progression-free survival and patterns of recurrence. QOL outcomes will be analyzed using mixed models for longitudinal data. Progression-free survival will be analyzed using standard methods for failure time data, primarily the Kaplan-Meier estimate. Progression-free survival is defined as the duration from the start of protocol treatment to the time of objective disease progression at any site or death in the absence of documented progression, while patients who have not progressed or died will be censored at the time of last follow-up. Differences between patient subgroups may be explored by the log-rank test, using exact methods as the event numbers will be modest. Patterns of recurrence will be reported descriptively.

14.5 Reporting and Exclusions;

All patients starting protocol therapy will be analyzed and reported for all study endpoints, whether or not treatment is completed.

14.5.1 Evaluation of toxicity.

All participants will be evaluable for toxicity from the time of their first treatment.

14.5.2 Evaluation of response. N/A. Patients with measurable disease are ineligible.

14.5.3 Evaluation of cancer control. At or before each scheduled follow-up surveillance visit patients will be categorized as clinically cancer-free, alive with cancer, dead from cancer, dead from complications of therapy, or dead from intercurrent illness, or cause of death unknown.

14.5.4 Pattern of cancer recurrence: In patients developing cancer recurrence, the pattern of recurrence will be recorded according to the criteria in 10.2 for local, regional and distant sites. As a patient may recur at multiple sites and at different times, the dates of recurrence will be recorded for each site. Progression-free survival will be based on the date of the earliest date of documented recurrence.

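### Sections 5.6 and 5.7 give conflicting follow-up rules for patients who stop treatment for an unacceptable adverse event, and one reading would lose their late-toxicity data

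*Combined protocol and SAP*

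**What the plan says.** Section 5.5 lists the reasons for ending treatment. One of them is "Unacceptable adverse event(s), including grade 4 thrombocytopenia or neutropenia; grade 3 hemoglobin, diarrhea, urinary frequency, or fatigue; or grade 2 weight loss". Section 5.7 turns each of these reasons into an exit from the study: "Participants will be removed from study when any of the criteria listed in Section 5.5 applies".

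Section 5.6 then has three sentences on follow-up:

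- General rule: "Participants will be followed for 60 months after completion of protocol therapy or removal from study or until death, whichever occurs first".
- Adverse-event removals: "Participants removed from study for unacceptable adverse events will be followed until resolution or stabilization of the adverse event".
- Recurrence: "Participants who experience a recurrence of their disease will be followed for survival only after the recurrence".

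Other sections bear on the same patients:

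- Section 6 collects adverse events up to the final study visit. Contact after the off-study visit is optional and concerns toxicity that is still continuing.
- Section 11.1 collects adverse events for 60 months from the last dose, and follows ongoing events beyond that.
- The last sentence of Section 14.2 reads: "All patients will be followed for a minimum of 60 months following completion of protocol therapy".
- Section 14.5 reads: "All patients starting protocol therapy will be analyzed and reported for all study endpoints, whether or not treatment is completed".
- Section 15.1.4 ties the final publication to at least 5 years of follow-up, or death, in all patients.

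**The concern.** The second sentence of 5.6 names a different end of follow-up for one group of patients and does not say how it relates to the sentence before it. A site could take it as a further duty (follow the event until it settles, within or beyond the 60 months) or as the specific rule that overrides the general one.

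Under the overriding reading, relapse-free patients who stopped for acute toxicity would leave once that toxicity settled. Delayed complications are part of a primary objective (1.2.2), and Section 1 also aims to relate acute and late toxicity to the volume of normal tissue irradiated. Patients with severe acute effects carry information about that relation. In a study of 22, each patient lost is 1/22 = 4.5% of the data. Visits that were never recorded cannot be reliably reconstructed later.

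**Working it through.** **1. The plan's own design figures.** The rule in 14.1 accepts the proton plan if at least 20 of 22 patients have a bowel dose-volume area at least 25% smaller. Exact binomial calculation:

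- Power = P(X ≥ 20 | n = 22, p = 0.95) = 0.905 (stated 91%).
- Type I error = P(X ≥ 20 | n = 22, p = 0.80) = 0.154 (stated 15%).

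Both reproduce. The histograms come from treatment plans, so follow-up rules do not touch these figures. The protocol states no sample size, target or precision for late toxicity.

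**2. The passages side by side.**

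| Section | Follow-up of a patient removed for an adverse event |
|---|---|
| 5.6, sentence 1 | 60 months after removal, or until death (natural reading) |
| 5.6, sentence 2 | Until the event settles |
| 6 | Contact after the off-study visit optional |
| 11.1 | Adverse events for 60 months from last dose, longer if ongoing |
| 14.2 | At least 60 months, counted from completing therapy, which this patient does not do |
| 14.5 | Analysed for all endpoints |
| 15.1.4 | At least 5 years or until death |

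Sections 11.1, 14.5 and 15.1.4 point to full follow-up. Section 6 and the starting point of the clock in 14.2 leave the shorter reading open.

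**3. Timing under the replacement reading.**

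- Section 6.1: "Recovery from acute side effects is expected over a 3-6 week period after the last treatment has been administered".
- First follow-up visit (9.3): 3 months ± 4 weeks, or about 13 ± 4 = weeks 9 to 17.
- First post-treatment quality-of-life assessment (9.4, note 7): 6 months.
- Late complications (2.3): months to years after radiation. Section 15.1.3 expects most symptomatic ones to show within 24 months.

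An event that settles by week 6 closes follow-up before the earliest date of the first visit, week 9.

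**4. Illustration of size.** All rates here are assumptions; the protocol gives none. Let k of 22 patients stop early, with a late-complication rate of 10% in the other 22 − k and RR × 10% in the k.

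- True rate = [(22 − k) × 0.10 + k × RR × 0.10] / 22
- Shown if the k count as event-free = (22 − k) × 0.10 / 22
- Shown if the k are left out = 10%

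| k | True, RR = 1 | True, RR = 3 | k counted as event-free | k left out |
|---|---|---|---|---|
| 2 | 10.0% | 2.6/22 = 11.8% | 2.0/22 = 9.1% | 10.0% |
| 4 | 10.0% | 3.0/22 = 13.6% | 1.8/22 = 8.2% | 10.0% |
| 6 | 10.0% | 3.4/22 = 15.5% | 1.6/22 = 7.3% | 10.0% |

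At equal risk (RR = 1), leaving the k out gives the right rate with less precision. For k = 4 the standard error grows by √(22/18) = 1.11. If early stoppers had a lower late risk, say RR = 0.5, the true rate for k = 4 would be (1.8 + 0.2)/22 = 9.1%, and leaving them out would overstate it.

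**The case against.** The case for full follow-up is strong. The adverse-event sentence contains no word of restriction, whereas the recurrence sentence right after it does, so the drafters knew how to restrict. Section 11.1 uses a similar formula about events settling, and there it extends the 60 months. With 14.5 and 15.1.4, this makes full follow-up the likelier intent.

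It does not remove the ambiguity. If the sentence only adds to the 60 months, it does little, because 11.1 already covers events that run longer. It is a specific rule next to a general one, and the recurrence sentence beside it is itself an exception to the general rule. Section 5.6's first sentence can even be parsed so that removal ends follow-up, though that is less natural.

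A reader might infer three stronger points, and the protocol supports none of them:

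- *That the plan definitely ends follow-up when the event settles.* It can be read that way; it does not say so.
- *That these patients have the highest late risk, so the estimate must favour protons.* Section 2.3 ties both acute and late effects to volume, total dose and dose per fraction, but does not rank early stoppers. A patient who stops early has also received less total dose.
- *That the main result is at risk.* Section 14 names the dose-volume comparison as primary and lists delayed complications among additional endpoints, with no test attached.

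Two cautions on timing also stand. The 3-6 weeks is a general expectation, not a statement about the grade 3-4 events that stop treatment. Weight loss, one of the triggers, appears in 6.1 as a slow, delayed effect.

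**Conclusion.** The concern holds as an unresolved conflict between follow-up rules. If the second sentence of 5.6 is applied as a replacement, patients whose acute event settles as expected could leave before the first visit, with no late-complication or post-treatment quality-of-life data and little recurrence data, while 14.5 still counts them for every endpoint.

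The bias cannot be sized from the protocol, which gives neither the number of early stoppers nor a late-complication rate. With 4 stoppers and a 10% rate in everyone (both assumed), the estimate is 8.2% instead of 10% if they are counted as event-free, a handling that 14.5 does not specify. It is unbiased but less precise if they are left out. A larger bias needs a difference in late risk, in either direction, that the protocol does not establish. The primary endpoint, its power and its type I error are unchanged. The change is still worth making, because delayed complications are a stated objective, the study is small and the remedy is wording.

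**What to change.** - **5.7:** separate discontinuation of protocol treatment from removal from study, so that meeting a 5.5 criterion ends treatment but not follow-up.
- **5.6:** make the adverse-event sentence additive. These patients stay on the 9.3/9.4 calendar (toxicity, quality of life, cancer status) to 60 months after stopping treatment, subject to the existing provisions for recurrence, death and withdrawal of consent. Unresolved events are followed longer, as in 11.1.
- **14.2:** run the 60 months from completion or discontinuation of therapy.
- **12.1.2:** record the off-treatment and off-study dates separately. The protocol lists one combined form for both; its content is not shown, so it may already hold two dates.

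If the sponsor does intend shorter follow-up for this group, 5.6 should say so and Section 14 should state how the analysis handles the loss. The stopping criteria in 5.5 are not changed. The cost is a wording amendment and a few more follow-up forms; Section 1.1 describes monitoring as essentially usual practice, so the added burden should be small.

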6. EXPECTED TOXICITIES AND DOSING DELAYS/DOSE MODIFICATIONS

Dose delays and modifications will be made using the following recommendations. Toxicity assessments will be done using NCI Common Terminology Criteria for Adverse Events (CTCAE v4.02 from 9/15/2009) which is available at <http://ctep.cancer.gov/reporting//ctc.html>.

All adverse events experienced by participants will be collected from the time of the first dose of study treatment, through the study and until the final study visit. Participants continuing to experience toxicity at the off study visit may be contacted for additional assessments until the toxicity has resolved or is deemed irreversible.

CONFIDENTIAL

This document is confidential. Do not disclose or use except as authorized.

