7. DRUG FORMULATION AND ADMINISTRATION: N/A

8. CORRELATIVE/SPECIAL STUDIES: N/A

9. STUDY CALENDAR

9.1 Baseline hematologic evaluations are to be conducted within 2-weeks prior to study entry. Scans must be done \leq 10 weeks prior to study entry.

9.2 Patients will be interviewed and examined weekly during treatment.

9.3 Routine surveillance follow-up will be: 3, 6, 9, 12, 15, 18, 21, 24, 28, 32, 36, 42, 48, 54 and 60 months (+/- 4 weeks) following adjuvant radiation treatment.

CONFIDENTIAL

This document is confidential. Do not disclose or use except as authorized.

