9.4 Study Calendar/Required Data

Tests and Observations	At Study Entry	During Treatment	At Follow Up (1)
Informed Consent	x		
History	x		x
Concurrent Meds	x	x	x
Physical Exam (2)	x	x	x
Pelvic Exam (3)	x	x	x
CBC with diff, PLT (4)	x	x	
Serum Chemistries (5)	x	x	
Toxicity and AE evaluation	x	x	x
Radiological imaging (6)	x		x
Quality of Life (7)	x		x

Notes:

- (1) Follow up schedule (+/- 4 weeks for each time point): every 3 months for 2 years; every 4 months to year 3; every 6 months until year 5.
- (2) Physical includes, weight, vitals, performance status required at baseline. For weekly on-treatment and follow up visits, physical exam will be performed as pertinent at the discretion of the treating physician, and includes weight. .
- (3) Pelvic Exam pre-study, during vaginal brachytherapy (typically week 6 of treatment) and at each follow up visit
- (4) Study entry labs for pre-treatment must be done within 14 days of study entry. Labs may be repeated twice weekly for uterine cancer patients, once weekly for cervix cancer patients during treatment to ensure maintenance of platelets >35,000mcL and ANC >800mcL. These labs are ordered and monitored at the discretion of the treating physician.
- (5) Required chemistries are: Albumin, Alk Phos, T bili, BUN, bicarbonate, chloride, creatinine, glucose, LDH, phosphorus, potassium, total protein, SGOT, SGPT, sodium, calcium, magnesium. These will be ordered and monitored at the discretion of the treating physician.
- (6) Contrast enhanced CT scan of the chest, abdomen and pelvis pre-study (\leq 10 weeks of study entry) and in post treatment, twice per year to year 3.
- (7) Quality of Life will be assessed using the FACT-En Version 4 (Appendix 2) instrument for uterine patients and the FACT-Cx Version 4 (Appendix 3) instrument for cervix patients. QOL will be assessed at study entry, and at 6, 12, 24, 36, 48, and 60 months (+/- 4 weeks) after protocol therapy.

10. MEASUREMENT OF EFFECT: Participants are excluded if they have measurable disease following hysterectomy. (3.2.2, 3.2.3)

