10.3 Quality of Life

Quality of life will be assessed at 6, 12, 24, 36, 48, 60 months following protocol therapy.

QOL will be assessed using the FACT-En Version 4 instrument for uterine patients and the FACT-Cx Version 4 for cervix patients.

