11. ADVERSE EVENT REPORTING REQUIREMENTS

11.1 General

Adverse event collection and reporting is a routine part of every clinical trial. This study will use the descriptions and grading scales found in the NCI Common Terminology Criteria for Adverse Events (CTCAE) version 4.02 9/15/2009 that is available at <http://ctep.cancer.gov/reporting//ctc.html>.

CONFIDENTIAL

This document is confidential. Do not disclose or use except as authorized.

Information on all adverse events, whether reported by the participant, directly observed, or detected by physical examination, laboratory test or other means, will be collected, recorded, followed and reported as described in the following sections.

Adverse events experienced by participants will be collected and reported from initiation of study treatment, throughout the study, and within 60 months of the last dose of study medication. Participants who experience an ongoing adverse event or related to a study procedures and/or study medication beyond 60 months will continue to be contacted by a member of the study team until the event is resolved, stabilized, or determined to be irreversible by the participating investigator.

Participants should be instructed to report any serious post-study event(s) that might reasonably be related to participation in this study. The investigator should notify the IRB and any other applicable regulatory agency of any unanticipated death or adverse event occurring after a participant has discontinued or terminated study participation that may reasonably be related to the study.

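### Section 5.6 stops disease follow-up at the first recurrence, but section 14.5.4 needs dates for later recurrence sites; the plan also does not say whether QOL and adverse-event collection stop

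*Combined protocol and SAP*

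**What the plan says.** Section 5.6 sets a 60-month follow-up, ended earlier only by death, and then makes a special rule: "Participants who experience a recurrence of their disease will be followed for survival only after the recurrence".

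Section 14.5.4, on the pattern of recurrence, says: "As a patient may recur at multiple sites and at different times, the dates of recurrence will be recorded for each site". It bases PFS on the earliest documented recurrence. Section 10.2 classes as local any cancer found in the target volume at any time after treatment starts; it does not restrict this to the first failure.

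Four other places set schedules with no mention of relapse:
- Section 9.3: "Routine surveillance follow-up will be: 3, 6, 9, 12, 15, 18, 21, 24, 28, 32, 36, 42, 48, 54 and 60 months".
- Section 10.3: "Quality of life will be assessed at 6, 12, 24, 36, 48, 60 months following protocol therapy". Note 7 to the calendar in section 9.4 agrees: "QOL will be assessed at study entry, and at 6, 12, 24, 36, 48, and 60 months".
- Section 11.1: adverse events "will be collected and reported from initiation of study treatment, throughout the study, and within 60 months of the last dose of study medication".
- Section 6: adverse events are collected from the first dose "through the study and until the final study visit".

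Section 14.5 analyses every patient who starts therapy for every study endpoint. Section 14.4 specifies mixed models for QOL and gives no rule for data that stop at recurrence.

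**The concern.** Dating a recurrence site that appears after the first one is disease follow-up, and a rule confined to survival excludes it. Site staff could follow 5.6 and never collect what 14.5.4 says will be recorded.

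The outputs at stake are stated aims. Section 14 lists cancer control within the irradiated volumes as an additional endpoint. Patterns of recurrence and QOL are secondary endpoints, and delayed complications are part of objective 1.2.2. For in-field control, the important patient is one whose first failure is distant and whose pelvic or para-aortic failure comes later. Under 5.6 that patient would be counted as controlled within the field.

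For QOL and late toxicity the problem is that the plan does not say which rule holds. If collection stops at relapse, whether data are missing depends on disease status, and no analysis can recover what was not collected.

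**Working it through.** **1. The plan's own figure.** The plan gives no number on this point. Its only design figure is the DVH rule in section 14.1 (at least 20 successes among 22). With X binomial, P(X ≥ 20) = p^22 + 22(1−p)p^21 + 231(1−p)²p^20.
- p = 0.95: 0.9052, against 91% stated.
- p = 0.80: 0.1545, against 15% stated.

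Both reproduce. The DVH comparison comes from treatment plans, so nothing after recurrence changes it.

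**2. Section 5.6 against sections 14.5.4 and 10.2, by order of failure.**
- All sites found together at first recurrence: both rules are met and every site is dated.
- In-field first, another site later: in-field failure is captured; the later site is lost from patterns of recurrence.
- Another site first, in-field later: the in-field failure is lost, although 10.2 would class it as local and 14.5.4 would date it. This is the case that touches in-field control.
- PFS: unaffected, because it uses the earliest recurrence, or death without progression.

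The reference in 14.5.4 to different times means it cannot be confined to sites present at the first recurrence.

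**3. Scheduled records at stake if QOL and visit-based toxicity collection stop at relapse.** Inputs are the 15 visits in section 9.3 (3, 6, 9, 12, 15, 18, 21, 24, 28, 32, 36, 42, 48, 54, 60) and the 6 post-treatment QOL times in section 10.3 (6, 12, 24, 36, 48, 60). For relapse at month r and survival of s months afterwards, count the time points after r and up to min(60, r + s). The documents do not give s; 24 and 12 months are assumptions that show the range.

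| Relapse month r | Alive at month 60: visits / QOL lost | s = 24: visits / QOL lost | s = 12: visits / QOL lost |
|---|---|---|---|
| 6 | 13 / 5 | 7 / 2 | 4 / 1 |
| 12 | 11 / 4 | 7 / 2 | 4 / 1 |
| 24 | 7 / 3 | 5 / 2 | 3 / 1 |

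Section 15.1.3 expects most symptomatic late complications within 24 months. Of the 8 visits up to month 24, relapse at month 6, 12 or 24 loses at most 6, 4 or 0.

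**4. Share of the cohort.** One patient is 1/22 = 4.5%. The documents give no recurrence rate. If it were 10% to 40% (an assumption), 22 × 0.10 = 2.2 and 22 × 0.40 = 8.8, so about 2 to 9 patients would move to survival-only follow-up. Patients with a missed later in-field failure would be a subset of these.

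**The case against.** The strongest reply concerns QOL and adverse events. Section 5.6 is a specific rule for relapsed participants, the schedules in 9.4, 10.3 and 11.1 are general, and a specific rule ordinarily governs. The end point in section 6, the final study visit, fits that reading too. Stopping at relapse is also defensible on its merits: later therapy confounds toxicity and QOL, and section 5.2.20d allows investigational agents after recurrence. This stands. It means that the documents support a request to reconcile the passages and state the data handling, but not a finding that collection must continue. It does not help with 14.5.4, whose text addresses recurrence after recurrence directly.

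A reader might infer three stronger points that the documents do not support:
- That 5.6 also conflicts with section 14.5.3, under which "At or before each scheduled follow-up surveillance visit patients will be categorized as clinically cancer-free, alive with cancer", or dead by cause. Survival follow-up can supply that status, and the combined follow-up and survival form in section 12.1.2 may follow a visit or a call.
- That all toxicity after relapse is lost. Section 11.1 has participants told to report serious later events that may be related to the study, and sections 6 and 11.1 allow continued contact about ongoing toxicity. What may be lost is scheduled collection of new, mainly non-serious, late toxicity.
- That every patient's first in-field failure is safe because first recurrences are recorded. It is safe only when it is, or accompanies, the first recurrence.

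**Conclusion.** The contradiction between 5.6 and 14.5.4 is real and should be fixed. Followed as written, 5.6 leaves later recurrence sites unrecorded, so local failures could be undercounted in the in-field control endpoint and patterns of recurrence would be incomplete. Each missed in-field failure is 4.5% of a cohort of 22.

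For QOL and late toxicity the finding is narrower: the plan does not say whether collection stops at relapse. The upper limits of 13, 11 or 7 visits and 5, 4 or 3 QOL assessments assume that collection stops and that the patient lives to month 60; shorter survival reduces them. They count records and do not measure bias. No bias size can be given, because the documents state no recurrence rate and name no estimator for late toxicity. A reader should not infer that the main result is at risk: the DVH endpoint, N=22, PFS and survival do not depend on this rule.

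**What to change.** Amend 5.6 so that, after a first recurrence, the site and date of later recurrences are still recorded from routine-care data to 60 months or death, with no extra protocol scans or examinations.

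Reconcile 5.6 with 10.3, calendar note 7 and 11.1 by stating whether QOL and late-toxicity collection continue after recurrence.
- If they continue: flag data obtained after salvage therapy and add a sensitivity analysis censored at the start of salvage.
- If they stop: say so in those sections, and state that late-toxicity and QOL results are limited to the recurrence-free period.

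The cost is one wording amendment and modest extra data capture in relapsed patients only. If full collection continues, this is at most 13 visit records and 5 questionnaires for a patient who relapses at month 6 and lives to month 60. Records will be less complete for patients treated elsewhere, and toxicity after salvage is harder to attribute.
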